9.3.4 Safety analysis

Safety and toxicity will be evaluated on the safety population by means of descriptive statistics during each study phase. Summary statistics (counts, %) will report the incidence of the AEs by CTC toxicity grade, dose level, cycle of therapy, relationship to study drug and overall. Counts and percentages will be produced for the results of the ECG, laboratory values, vital signs, physical examination, all classified as Normal/Abnormal NCS/Abnormal CS by dose level and therapy cycle.

Descriptive statistics will also be produced for the extent of exposure, overall drug(s) administration, drug(s) administration by dose(s) level, and dose(s) delay by dose(s) level.

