who, throughout the study, experienced DLT events that clearly started during the infusion and that were characterized by increased transaminases, with or without severe coagulation derangements and multiorgan failure A panel of widely acknowledged AML experts was also called to advice on the pathophysiology of the above events as well as on the next steps for the prosecution of the clinical development of MEN1112 in AML. The experts concluded that the pathophysiology of the severe events observed so far in the above patients may involve cytokine storm and/or monocytic-macrophage activation, as well as massive lysis of target cells and that, to possibly prevent the occurrence of such events or limiting their severity, general safety measures should be applied. Based on the experience with other compounds (e.g. Blinatumomab, Venetoclax) and on the fact that the above toxicities did develop either at the first or the second dose during the first cycle of treatment, a "ramp-up" approach during Cycle 1 was concluded to be the most appropriate one. Therefore, the dose escalation will be resumed from the 1.7 mg/kg dose level (i.e. from the MTD achieved using the "one shot" schedule per Protocol V4.1), under the 3+3 design and using a "ramp-up" approach during the first two MEN1112 administrations of Cycle 1. If no DLT occurs, additional dose levels will be explored at 2.0 mg/kg, 3.0mg/kg and 5.0mg/kg.

Additional intermediate dose levels may be also explored, under a 3+3 design, upon recommendation of the iDSMB that will be appointed to guide dose escalation decisions. In addition, as the clinical data collected so far are not sufficient to adequately design a maintenance treatment phase, starting from protocol version 6.1/6.2 the study will no longer encompass a maintenance phase, which is replaced by a follow-up period for safety and efficacy assessments. To serve the best interest of the patients, for those achieving at least a partial response according to protocol-defined criteria, the Sponsor commits to consider providing MEN1112 to allow the prosecution of the infusions at the frequency recommended by the iDSMB on an individual basis and after discussion with the treating Investigator and the Medical Monitor.

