8.2.1 Inclusion criteria

Inclusion criteria will be evaluated during Screening Period, with the exception of inclusion criteria 3 and 4, which will be evaluated at Visit 1/Day 1; inclusion criteria 5 and 6 will be re-evaluated prior to the first study drug administration (Visit 1/Day 1).

- 1. Male or female patients aged \geq 18 years.
- 2. Documented definitive diagnosis of AML (according to World Health Organization (WHO) criteria, 2008) that is relapsed /refractory to standard treatment, for which no standard therapy is available or the patient refuses standard therapy. For the purpose of this study, refractory AML is defined as following:

Failure to achieve CR/CRi (IWG criteria, 2003) following at least 1 cycle of cytotoxic chemotherapy (or hypomethylating agents if unsuitable for cytotoxic chemotherapy) and unlikely, as per Investigator's judgement, to achieve CR/CRi with further cytotoxic chemotherapy (or hypomethylating agents if unsuitable for cytotoxic chemotherapy).

- 3. WBC count \leq 10 x 109/L at Visit 1; hydroxyurea is allowed to lower WBC count.
- 4. ECOG performance status of 0 to 2 at Visit 1/Day 1.
- 5. Life expectancy of at least 2 months.
- 6. Adequate renal and hepatic laboratory assessments:
 - AST, ALT, ALP $\leq 3.0 \times$ ULN, unless considered due to leukemic organ involvement.
 - Total Bilirubin $\leq 2.0 \times ULN$.
 - Serum creatinine $\leq 2.0 \times \text{ULN}$.

- 7. A female of childbearing potential may be enrolled providing she:
 - has a negative pregnancy test during screening period and
 - is routinely using an effective method of birth control that both results in a Pearl index < 1 and is considered highly effective as defined by the Clinical Trial Facilitation Group (e.g. combined estrogen and progestogen containing hormonal contraception, associated with inhibition of ovulation, intrauterine device, total sexual abstinence or bilateral tubal occlusion) until 6 months from the last study drug administration
 - undergoes a monthly pregnancy test until 6 months from the last study drug administration.
- 8. Able to give written informed consent before any study related procedure.

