8.5.2.6 Clinical laboratory evaluation

Safety laboratory assessments will be performed at each study visit except at Visit 5-6, Visit 28-29 and during End of Treatment. Pregnancy test will be performed, if applicable, during Screening Period, at Visit 11, at Visit 27, at Visits 35-38 and at the End of Study Visit. In addition, female patients of childbearing potential are required to undergo a monthly pregnancy test until 6 months from the last study drug administration. Urinalysis will be assessed prior to and at the end of the first "ramp-up" administration visit (Visit 1/Day 1, Visit 2/Day 2 and Visit 3/Day 3). The assessment of anti-HIV antibodies, anti-HBcAg antibodies, HBV-DNA and HCV-RNA will be performed ONLY during the Screening Period. Safety tests will be performed by the local laboratory of participating sites in order to ensure prompt patient management. For the same reason, tests for anti-HIV antibodies, anti-HBcAg antibodies, HBV-DNA and HCV-RNA will be performed by the local laboratory of participating sites according to local standard procedures. Results of laboratory tests for anti-HIV antibodies, anti-HBcAg antibodies, HBV-DNA, HCV-RNA which have been performed within 3 months prior to Screening Period in the context of the standard patient's management (either in the local lab or in a different lab, provided that they comply with local standard procedures) can be reported in the e-CRF under Screening Period procedures. In such case, there is no need to repeat the above mentioned tests. Laboratory values have to be transcribed into the e-CRF, except for the urinalysis where only the

judgment will be reported; the Sponsor will be provided by the site laboratories with the currently valid version of the respective normal ranges (any update of reference ranges needs to be notified on an ongoing basis).

The lab print-outs should be identified with the patient number. All print-outs should be dated and signed by the Investigator and stored in the patient's record. Any out of range value shall be clinically assessed by the Investigator.

The volume of blood to be drawn for each battery of safety lab tests will amount to approximately 15 mL.

The following tests will be performed:

SERUM CHEMISTRY	SERUM VIROLOGY	HAEMATOLOGY	URINALYSIS
Creatinine	Anti-HIV antibodies	Haemoglobin	pН
Uric acid	Anti-HBcAg antibodies	Haematocrit	Density
Potassium	HBV-DNA	RBC count	
Phosphorus	HCV-RNA	Platelet count	
		MCV	
Calcium		WBC count and	Nitrite

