9.3 STATISTICAL ANALYSIS

9.3.1 Descriptive statistics

All study variables (with the exception of PK variables) will be presented by cohort, dose and overall, by using the appropriate descriptive statistics according to the variable nature, unless otherwise specified:

- Continuous variables: number of non-missing observations, arithmetic mean, standard deviation (SD), minimum, median, maximum.
- Categorical variables: number of non-missing observations and column percentages (N, %).
- Time to event variables: number of non-missing observations, number and percentage of censored observations, 1st quartile, median and its 95% CI, 3rd quartile, Kaplan-Meier survival curves and event rate every 21 days.

The behaviour over time of study variables will be summarised by cohort and overall as follows:

- Continuous variables: descriptive statistics for each time point and for the absolute/percentage differences to baseline.
- Discrete variables: descriptive statistics for each time point and shift tables to baseline.

The Overall Survival (OS) is calculated as:

- In case of all-cause death:
 - OS = date of death date of first study drug administration + 1.
- In case of censored information not for drop-out:
 - OS = date of end of observation period (i.e. study end / end of survival follow-up) date of first study drug administration + 1.
- In case of censored information for drop-out:
 OS = Last date known alive date of first study drug administration + 1.

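### Section 9.3.4 should add a programmed table of each patient's worst laboratory grade, because its three-class scale can miss worsening in patients who enter with abnormal liver or renal tests

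*Combined protocol and SAP*

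**What the plan says.** The safety section (9.3.4) plans two kinds of table that bear on laboratory toxicity. The adverse event tables "will report the incidence of the AEs by CTC toxicity grade, dose level, cycle of therapy". Then come counts and percentages for ECG and "laboratory values, vital signs, physical examination, all classified as Normal/Abnormal NCS/Abnormal CS by dose level and therapy cycle". No other laboratory classification is named there, and the unit counted (patient or result) is not stated. Under 8.5.2.6 the investigator assesses every out-of-range value clinically, so the split between the two abnormal classes is a site judgement.

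The general rules in 9.3.1 also apply: "All study variables (with the exception of PK variables) will be presented by cohort, dose and overall". The continuous statistics listed there include minimum, median and maximum. On time course, "The behaviour over time of study variables will be summarised by cohort and overall as follows", and for laboratory values the relevant line is "Continuous variables: descriptive statistics for each time point and for the absolute/percentage differences to baseline". Discrete variables get shift tables against baseline.

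On entry, inclusion criterion 6 (8.2.1) sets limits of 3.0 x ULN for AST, ALT and ALP, "unless considered due to leukemic organ involvement", and 2.0 x ULN for total bilirubin and creatinine. It sets no limit for coagulation tests.

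On data, 8.5.2.6 states: "Laboratory values have to be transcribed into the e-CRF". Urinalysis is the exception; only the judgement is recorded. The same section has the site laboratories supply their normal ranges to the sponsor.

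**The concern.** The ramp-up schedule was introduced after four patients had DLTs that section 6.3 describes as "characterized by increased transaminases, with or without severe coagulation derangements". The natural question for the new schedule is how many patients at each dose level reached a given peak severity in liver and coagulation tests, and from what starting point. A scale that runs from normal to abnormal, with the abnormal part divided by site opinion, has little room left for a patient who enters at 2.5 x ULN. If the final tables rely on it for laboratory data, real worsening may appear as no change of class. With many samples per patient and no stated denominator, the percentages may also not be percentages of patients.

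**Working it through.** The plan gives no figure for this point, so there is none to reproduce. The check has four parts.

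**1. Samples behind one cell of the table (Appendix III).**
- Cycle 1: Visits 1–3, 3 x 5 = 15; Visit 4, 1; Visits 8–10, 3 x 5 = 15; Visit 11, 1; Visit 12, 5; Visits 13–15, 3. Total 15 + 1 + 15 + 1 + 5 + 3 = 40, of which one is the Visit 1 pre-infusion sample.
- Cycle 2: Visits 16–27, 12; Visit 30, 1. Total 13.

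If results are counted, one fully sampled patient contributes 40 entries to a Cycle 1 percentage, and a patient who stops early contributes fewer.

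**2. What each planned table shows for a patient abnormal at entry.** The ALT values are assumed, for illustration. A cohort of 6 has baselines of 0.8, 1.0, 1.5, 2.5, 2.8 and 0.6 x ULN. Abnormal means above 1 x ULN, so 3/6 are abnormal. Only the fourth patient changes.

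| Fourth patient rises from 2.5 to (x ULN) | Abnormal before / after | Maximum change in 9.3.1 (x ULN) | Maximum % change |
|---|---|---|---|
| 5 | 3/6 / 3/6 | 5 − 2.5 = +2.5 | +100% |
| 8 | 3/6 / 3/6 | 8 − 2.5 = +5.5 | +220% |
| 12 | 3/6 / 3/6 | 12 − 2.5 = +9.5 | +380% |
| 20 | 3/6 / 3/6 | 20 − 2.5 = +17.5 | +700% |

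The normal/abnormal count never moves. The three-class table moves only if the site re-labels the patient from not clinically significant to clinically significant. The maximum change in 9.3.1 does move.

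**3. What 9.3.1 still leaves out.** It works one time point at a time. If two time points each show a maximum of 8 x ULN, the reader cannot tell one patient twice (1/6) from two patients once each (2/6), nor the baseline of either. The time-course summaries are by cohort and overall, with no worst value per patient or per cycle. The table above also uses multiples of ULN. Section 9.3.1 does not say that values will be scaled this way, although tests are local and the synopsis foresees about 20 sites.

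**4. What the adverse event tables leave out.** Under 8.6.3 a new or worsening laboratory abnormality is reported as an adverse event when the investigator considers it clinically significant. Under 8.5.2.7.3 the severity of a laboratory event may rest on the size of the abnormality, on interference with daily activities, or on both. The recorded grade therefore need not follow from the value, and the study is open label. No planned table is stated to derive grade from the values by program.

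**The case against.** The strongest reply is that the plan as a whole already shows worsening. Section 9.3.1 covers every non-PK variable, includes the maximum, and has absolute and percentage change from baseline; in Step 1 cohorts of three to six evaluable patients a large rise would stand out. Section 8.5.2.7.3 asks for the highest grade reached in each cycle, so for events judged significant the adverse event tables come close to a worst-grade table. Severe related non-haematological events in Cycle 1 also count as DLTs, the primary endpoint. The existing data support this. Section 6.2.4.2 reports grade 3 or higher related events in the Investigations class in 21.3% of patients (10/47), clearly more often at 2.5 mg/kg. It also reports disseminated intravascular coagulation in 60.0% (3/5) at that dose against 0–17.6% in earlier cohorts.

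Most of this stands, and it rules out four stronger readings that a reader might infer:
- that laboratory safety is tabulated only in three classes, which 9.3.1 contradicts;
- that the plan cannot show worsening, which 9.3.1, the graded adverse event tables and the DLT endpoint contradict;
- that the abnormal-at-entry argument extends to coagulation, although 8.2.1 sets no coagulation limit and the documents give no such baseline;
- that the iDSMB would see only these tables, although 8.4.3.1 gives it the latest safety data and leaves the format to a charter not included here.

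It is also fair that 9.5 defers detail to the SAP, and the file contains no separate SAP text. What the reply does not supply is a per-patient worst value that is independent of site judgement. The Investigations signal is for a whole system organ class, not for transaminases.

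**Conclusion.** The point holds as a modest improvement, not as an error. The only laboratory classification that 9.3.4 names is judged by the investigator, has no stated denominator, and can miss worsening in liver and renal tests for patients abnormal at entry. Section 9.3.1 and the adverse event tables show some of that worsening, but neither yields an objective worst grade per patient. No numerical bias can be attached to this: the share of patients who enter abnormal is not given, and the cohort of six uses assumed values. The conclusion assumes that the SAP does not already contain such a table; if it does, a cross-reference from 9.3.4 settles the matter. Nothing here affects the DLT or MTD definitions.

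**What to change.** In 9.3.4 and the SAP:
- Add a table, by dose level and cycle, of each patient's worst post-baseline CTCAE v4.03 grade against baseline grade. Derive it by program from the e-CRF values and local normal ranges, with patients as the denominator. Cover AST, ALT, ALP, bilirubin, creatinine, INR, PTT, fibrinogen, platelets and neutrophils.
- Report each patient's peak multiple of ULN for AST, ALT, ALP, bilirubin and creatinine, summarised by dose level and cycle.
- State which pre-dose sample is baseline, since there is one at screening and one before the Visit 1 infusion, and 9.3.1 does not choose.
- Keep the three-class table for ECG, vital signs and physical examination, and for urinalysis, where only the judgement is recorded. State that it counts patients.

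The cost is programming. Values and normal ranges are already collected under 8.5.2.6, no extra sample or visit is needed, and 9.5 has the SAP finalised before database lock.

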- Recording of AEs and change in concomitant medications

Visit 8/Day 8 (five days after the completion of Visit 3), Visit 9/Day 9 (one day after the completion of Visit 8) and Visit 10/Day 10 (one day after the completion of Visit 9), second 3-day "*ramp-up*" administration

Prior to study drug administration

- Physical examination, including vital signs
- Weight measurement (ONLY at Visit 8/Day 8)
- PS evaluation
- Blood sampling for safety lab test NOTE: Check that WBC count is ≤ 10 x 10⁹/L (ONLY at Visit 8/Day 8); hydroxyurea is allowed to lower WBC count.
- Blood sampling for PK (pre-infusion)
- Recording of AEs and change in concomitant medication
- TLS prophylaxis (see Appendix I: TLS Manual for Investigator)
- Premedication (see §8.4.2)

Study drug administration

- Study drug administration, given as a 6h infusion with constant infusion rate
- Blood sampling for safety lab test at the following time points after start of infusion: 2h, 4h, 8h, 12h
- Vital signs every 15 minutes during the first hour of study drug administration, after then at the same time points of blood sampling for safety lab test
- Blood sampling for PK
 at the end of infusion)
- Recording of AEs and change in concomitant medications

Visit 11/Day 11, one day after the completion of the entire second "ramp-up"

- Physical examination, including vital signs
- PS evaluation
- Blood sampling for safety lab test including pregnancy test, if applicable
- Recording of AEs and change in concomitant medications

Visit 12/Day 15, five days after Visit 10, first "one-shot" infusion

Prior to study drug administration

- Physical examination, including vital signs
- Weight measurement
- PS evaluation
- Blood sampling for safety lab test

NOTE: Check that WBC count is $\leq 10 \ge 10^{9}$ /L; hydroysurea is allowed to lower WBC count.

- Blood sampling for PK (pre-infusion)
- Recording of AEs and change in concomitant medications
- TLS prophylaxis (see Appendix I: TLS Manual for Investigator)
- Premedication (see §8.4.2)

Study drug administration

- Study drug administration, given as a 6h infusion with constant infusion rate
- Blood sampling for safety lab test at the following time points after start of infusion: 2h, 4h, 8h, 12h
- Vital signs every 15 minutes during the first hour of study drug administration, after then at the same time points of blood sampling for safety lab test
- Blood sampling for PK (at the end of infusion)

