- Recording of AEs and change in concomitant medications

Visit 13-15/Day 16-18, one, two and three days after Visit 12

- Physical examination including vital signs
- PS evaluation
- Blood sampling for safety lab test (at 24h, 48h and 72 h after start of infusion)
- Recording of AEs and change in concomitant medications

CYCLE 2

Visit 16/Day 22, seven days after Visit 12

Prior to study drug administration

- Physical examination including vital signs
- Weight measurement
- PS evaluation
- Blood sampling for safety lab test
- •
- Blood sampling for PK

(pre-infusion)

- Bone marrow aspirate for morphologic assessment,
- Recording of AEs and change in concomitant medications
- Premedication (see §8.4.2)

Study drug administration

- Study drug administration, given as a 6h infusion with constant infusion rate
- Vital signs every 15 minutes during the first hour of study drug administration and at 15 minutes after end of infusion
- Blood sampling for PK (at the end of infusion)
- Recording of AEs and change in concomitant medications

Visit 17-19/ Day 23-25, one, two and three days after the completion of Visit 16, respectively

- Physical examination including vital signs
- PS evaluation
- Blood sampling for safety lab test
- Recording of AEs and change in concomitant medications

Visit 20/Day 29, seven days after the completion of Visit 16

Prior to study drug administration

- Physical examination including vital signs
- Weight measurement
- PS evaluation
- Blood sampling for safety lab test
- Blood sampling for PK (pre-infusion)
- Recording of AEs and change in concomitant medication
- Premedication (see §8.4.2)

Study drug administration

- Study drug administration, given as a 6h infusion with constant infusion rate
- Vital signs every 15 minutes during the first hour of study drug administration and at 15 minutes after end of infusion
- Blood sampling for PK
 at the end of infusion
- Recording of AEs and change in concomitant medications

Visit 21-23/Day 30-32, one, two and three days after the completion of Visit 20, respectively

- Physical examination including vital signs
- PS evaluation
- Blood sampling for safety lab test
- Recording of AEs and change in concomitant medications

Visit 24/Day 36, seven days after the completion of Visit 20

Prior to study drug administration

Physical examination including vital signs

- Weight measurement
- PS evaluation
- Blood sampling for safety lab test
- Blood sampling for PK (pre-infusion)

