8.5.2.2 Physical Examinations and Vital signs

A complete physical examination will be performed at each study visit from Screening to End of Study Visit, except at Visit 5-6, Visit 28-29 and during the End of Treatment period; it includes a general appearance observation and a complete exam of the following body systems/areas: Head, Eyes, Ears, Nose and Throat (HEENT)/Neck, Lymph Nodes, Thyroid, Abdomen, Skin, Cardiovascular, Respiratory, Gastrointestinal, Neurological and Musculoskeletal/Extremities.

Vital signs will be recorded throughout the study at each visit except at Visit 5-6, Visit 28-29/ and during the End of Treatment period. At each study drug administration during Cycle 1, vital signs should be measured prior to study drug administration and following the same time points of blood sampling for safety lab tests (see 14.3). At Cycle 2, they should be measured prior to study drug administration, every 15 minutes during the first hour of study drug administration and 15 minutes after the end of infusion. The following parameters will be measured:

- Heart rate (HR, beats / min)
- Blood pressure (BP, systolic and diastolic, mmHg)
- Breathing rate (BR, breaths / min)
- Body temperature (T, °C).

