14.3 APPENDIX III: TIMINGS OF SAFETY BLOOD SAMPLING

		NR. SAFETY	TIMING
	STUDY VISIT	SAMPLES	
	SCREENING	1	N/A
			Pre-infusion
			2h after the start of infusion
	1, 2, 3	5 each Visit	4h after the start of infusion
			8h after the start of infusion
			12h after the start of infusion
	4	1	One day after the completion of the entire first
	+	1	ramp-up
			Pre-infusion
			2h after the start of infusion
	8, 9, 10	5 each Visit	4h after the start of infusion
CVCLE 1			8h after the start of infusion
CICLEI			12h after the start of infusion
	11	1	One day after the completion of the entire
	11	1	second ramp-up
		5	Pre-infusion
	12		2 h after the start of infusion
			4 h after the start of infusion
			8h after the start of infusion
			12 h after the start of infusion
	13, 14, 15	1 each Visit	24 h after the start of infusion
			48h after the start of infusion
			72 h after the start of infusion
	16	1	Pre-infusion
	17	1	N/A
	18	1	N/A
	19	1	N/A
	20	1	Pre-infusion
	21	1	N/A
CYCLE 2	22	1	N/A
	23	1	N/A
	24	1	Pre-infusion
	25	1	N/A
	26	1	N/A
	27	1	N/A
	30	1	N/A
FOLLOW-UP	25 20	1	N/A
PERIOD	33-30	1	
	End of study	1	N/A

14.4 APPENDIX IV: COMMON TERMINOLOGY CRITERIA FOR ADVERSE EVENTS (CTCAE) VERSION 4.0. PUBLISHED: MAY 28, 2009 (V4.03: JUNE 14, 2010). U.S.DEPARTMENT OF HEALTH AND HUMAN SERVICES - NATIONAL INSTITUTES OF HEALTH - NATIONAL CANCER INSTITUTE

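### By-cycle laboratory and AE tables lean toward an apparent fall in Cycle 2, because safety labs at 2 to 12 h after infusion start are scheduled only in Cycle 1

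*Combined protocol and SAP*

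**What the plan says.** Section 9.3.4 gives counts and percentages for ECG, laboratory values, vital signs and physical examination, "all classified as Normal/Abnormal NCS/Abnormal CS by dose level and therapy cycle". For adverse events, "Summary statistics (counts, %) will report the incidence of the AEs by CTC toxicity grade, dose level, cycle of therapy" and relationship to study drug. It does not say whether the unit is a record or a patient's worst value, gives no denominator, and does not refer to the sampling schedule.

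The schedule differs between cycles. Section 8.5.1 requires, at each Cycle 1 infusion, "Blood sampling for safety lab test at the following time points after start of infusion: 2h, 4h, 8h, 12h", in addition to a pre-infusion sample. After the first one-shot infusion (Visit 12), Visits 13 to 15 add "Blood sampling for safety lab test (at 24h, 48h and 72 h after start of infusion"). In Cycle 2, section 8.5.1 and Appendix III (14.3) schedule one pre-infusion sample at each of Visits 16, 20 and 24, one on each of the three days after, and one at Visit 30. No Cycle 2 lab is scheduled between the infusion and the next-day visit.

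Two further rules link labs to the AE table. Section 8.6.3 has clinically significant laboratory abnormalities reported as AEs, and section 8.5.2.7.3 has the e-CRF hold the worst grade within each cycle.

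**The concern.** A by-cycle table invites a comparison of cycles. Here the cycles are not observed in the same way, and they differ in the window that matters most. Section 6.3 describes four patients whose DLT events began while the drug was being infused, with raised transaminases and in some cases severe clotting disturbance. It also places most severe toxicities within 48 hours of the start of infusion. A laboratory change that appears and resolves before the next day can be seen in Cycle 1 and missed in Cycle 2.

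All three Cycle 2 doses are full one-shot infusions, so fewer abnormal labs or lab-detected AEs there could be taken as good tolerance of the full dose. Safety and tolerability is a secondary objective (7.2), and section 8.4.3.1 lets the iDSMB weigh Cycle 2 AEs in escalation decisions.

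**Working it through.** **1. Scheduled safety labs (8.5.1 and Appendix III).** Appendix III states 5 samples per Cycle 1 infusion visit. The visit text reproduces this: pre-infusion plus 2, 4, 8 and 12 h = 5.

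- Cycle 1: Visits 1–3, 15; Visit 4, 1; Visits 8–10, 15; Visit 11, 1; Visit 12, 5; Visits 13–15, 3. Total 40.
- Cycle 2: 3 × (1 + 3) + Visit 30 = 13.
- Samples at 2 to 12 h after infusion start: 7 × 4 = 28 v 0.
- One one-shot infusion with its next three days: 5 + 3 = 8 (Visits 12–15) v 1 + 3 = 4 (Visits 16–19).
- Days with at least one lab: 12 (Visits 1–4, 8–15) v 13 (Visits 16–27, 30).

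**2. Range of the effect on a worst-per-patient table.** Suppose each independent chance has the same probability p of a new clinically significant abnormality in both cycles, so there is no true change. The documents give no p; 1% and 2% are assumptions. P(at least one) = 1 − (1 − p)^n.

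| Assumption | n, Cycle 1 v Cycle 2 | p = 1% | p = 2% |
|---|---|---|---|
| Every sample independent | 40 v 13 | 33% v 12% | 55% v 23% |
| One chance per sampled day | 12 v 13 | 11.4% v 12.2% | 21.5% v 23.1% |

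For a single one-shot infusion at p = 2%, independence gives 1 − 0.98^8 = 15% v 1 − 0.98^4 = 8%. One chance per day gives 4 days v 4 days, so 8% in both.

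**3. Percentage of records.** If risk is the same at every time point, a percentage of records equals p in both cycles and does not fall. If risk is higher around the infusion, it does. With an assumed 2% at 2 to 12 h and 1% elsewhere, Cycle 1 shows (28 × 2% + 12 × 1%) / 40 = 1.7% and Cycle 2 shows 1.0%.

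**4. Which abnormalities are missed.** Assume onset evenly spread over the 6 h infusion. The Cycle 1 one-shot schedule always catches an abnormality lasting 4 h or more. In Cycle 2 the first later sample is on the next day, with no clock time given. If it falls 24 h after the start, anything lasting under 18 h is missed and anything over 24 h is caught. If it falls 24 h after the end (30 h after the start), those limits become 24 h and 30 h.

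**5. Vital signs.** Cycle 1 in section 8.5.1: "Vital signs every 15 minutes during the first hour of study drug administration, after then at the same time points of blood sampling" for labs, so with the pre-infusion reading 1 + 4 + 4 = 9 per infusion. Cycle 2: "Vital signs every 15 minutes during the first hour of study drug administration and at 15 minutes after end of infusion", so 1 + 4 + 1 = 6. Adding non-infusion visits, totals are 7 × 9 + 5 = 68 v 3 × 6 + 10 = 28, or 9.7 v 9.3 per infusion. Section 8.5.2.2 says only that in Cycle 1 "vital signs should be measured prior to study drug administration and following the same time points of blood sampling for safety lab tests", with no 15-minute readings. That gives 7 × 5 + 5 = 40 v 28, or 5.7 v 9.3 per infusion.

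**The case against.** A reader might infer that recorded toxicity must fall from Cycle 1 to Cycle 2 by construction, and take 55% v 23% as the estimate. The documents do not support that.

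- **Unit.** Section 9.3.4 leaves it undefined. Under a percentage of records with constant risk there is no fall.
- **Correlation.** Samples a few hours apart in one patient are serial readings. At one chance per sampled day the fall disappears, so 55% v 23% is an extreme.
- **Exposure.** Cycle 1 has 7 infusion days and Cycle 2 has 3. Per infusion, labs are 40/7 = 5.7 v 13/3 = 4.3.
- **Detection by other routes.** Labs on the three days after each Cycle 2 infusion pick up longer events, unscheduled tests are encouraged, and AEs are recorded at every visit.
- **A real fall.** Section 6.3 places the severe toxicities at the first or second dose.
- **Selection.** Patients in Cycle 2 are those who got through Cycle 1. Under the one-shot schedule, 22 of 47 treated patients completed Cycle 1 with the post-cycle tests needed for the efficacy population (Table 1). Matching time points alone does not remove this.
- **Existing plan.** Section 9.3.1 already promises summaries at each time point and shift tables, and no formal comparison of cycles is planned.

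All of these stand as limits on size. They do not remove the direction of the bias for short-lived laboratory changes. The time-point summaries in 9.3.1 do not correct the by-cycle AE and abnormality tables in 9.3.4, and the undefined unit is itself something to settle.

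**Conclusion.** The by-cycle laboratory and AE summaries, if raw or worst-per-patient, are biased toward fewer recorded abnormalities in Cycle 2. The firm part is the schedule: 28 v 0 samples at 2 to 12 h, and 8 v 4 labs for a like-for-like one-shot infusion. The size is not known. At an assumed 2% risk it lies between no fall and 55% v 23%, depending on how strongly serial samples are correlated. The bias concerns abnormalities that resolve within about a day and prompt no unscheduled test.

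Two wider inferences fail. Vital signs are not comparably affected: per-infusion counts are close under 8.5.1 and reverse under 8.5.2.2. The dose-finding result is not biased by this, because the DLT definition is confined to Cycle 1. This is a weakness in a secondary descriptive analysis, worth correcting before the SAP is final.

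**What to change.** In section 9.3.4 or the SAP, which section 9.5 says is finalised before database lock:

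1. State the counting unit and denominator of every by-cycle table.
2. Base the Cycle 1 v Cycle 2 laboratory table on one-shot infusions at common time points: pre-infusion and 1, 2 and 3 days after (Visits 12–15 v 16–19, 20–23 and 24–27). Count per patient per infusion, with patients assessed as the denominator. The per-infusion unit is needed because the matched set holds 4 labs in Cycle 1 and 3 × 4 = 12 in Cycle 2, which would otherwise reverse the imbalance.
3. Repeat that table in patients dosed in both cycles, to limit selection.
4. Report the 2 to 12 h labs in a separate table labelled as Cycle 1 only.
5. In the by-cycle AE table, show lab-detected AEs separately from clinical AEs.
6. For vital signs, reconcile 8.5.1 with 8.5.2.2 on the Cycle 1 15-minute readings, then limit any by-cycle comparison to readings common to both cycles.

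The cost is SAP wording and a few extra tables, with no added sampling. The matched comparison uses 4 of the 40 Cycle 1 labs, so it is less precise and says nothing about the ramp-up days.
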